9.4. Background and Demographic Characteristics

Subjects' age, height, weight, and baseline characteristics will be summarized using descriptive statistics, while gender and other categorical variables will be provided using frequency tabulations by dose cohort. Medical history data will be summarized using frequency tabulations

by the Medical Dictionary for Regulatory Activities (MedDRA) system organ class and preferred term. MDS diagnoses will be summarized using frequency tabulations.

9.5. Subject Disposition

Subject disposition (analysis population allocation, entered, discontinued, along with primary reason for discontinuation) will be summarized using frequency and percent for both treatment and follow-up phases. A summary of subjects enrolled by site will be provided. Protocol deviations will be summarized using frequency tabulations.

9.6. Efficacy Analysis

9.6.1. Primary Efficacy Analysis

The primary efficacy endpoint of HI-E per IWG ([Cheson, 2006](#)) within 24 weeks is defined as proportion of subjects meeting HI-E criteria of ≥ 1.5 g/dL increase in Hgb sustained over any consecutive 56-day period in the absence of RBC transfusions from W1D1 through Week 24. Subjects discontinued from the Treatment Period without achieving HI-E will be counted as non-responders.

As the primary efficacy analysis, one sample binomial one sided exact test will be performed based on ITT population, to provide p-value (significance level: 0.025). The statistical hypothesis will be as follows,

$$H_0: p \leq 10\%,$$

$$H_a: p > 10\%$$

where p denotes the true response rate. The number and percentage of subjects who achieve the response and 95% CI will be presented based on the ITT population.

Dose modification guidance for luspatercept in Section [7.2.2](#) defines that, if predose Hgb is ≥ 12.0 g/dL at the day of dosing, the dose should be delayed until Hgb is < 11.0 g/dL. For subjects who meet this criterion and then have their dose delayed, if their Hgb levels temporarily decrease to < 1.5 g/dL but achieve ≥ 1.5 g/dL again after treatment resumption, this period (ie, the time from dose delay to achieving a Hgb increase of ≥ 1.5 g/dL again) will be included as the period of sustained Hgb increase of ≥ 1.5 g/dL. As a sensitivity analysis, the analysis results not applicable to this rule will also be calculated.

Additional details will be outlined in the SAP.

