AE = adverse event; Hgb = hemoglobin; IP = investigational product; IWG = International Working Group; MDS = myelodysplastic syndromes; RBC = red blood cell.

^a Possibly, probably or definitely related to IP.

^b Includes systolic blood pressure ≥ 160 mmHg and diastolic blood pressure ≥ 100 mmHg.

^c If dose delay is > 12 consecutive weeks (> 15 weeks from last dose administered), treatment should be discontinued.

^d Predose Hgb value not being influenced by RBC transfusion (ie, Hgb result > 14 days after last RBC transfusion or within 3 days from next RBC transfusion); Hgb should be rechecked weekly during dose delay.

^e Upper limit of normal $> 10,000$ total WBC/ μ L or as defined by institutional standards.

^f Peripheral blood smear should be prepared for central pathology lab assessment.

^g At the investigator's discretion, bone marrow samples may also be collected and analyzed centrally to assess MDS disease status (eg, cytromorphology) prior to making decision regarding treatment discontinuation. The central laboratory must also confirm $< 5\%$ bone marrow blasts prior to resumption of treatment.

^h The investigator may contact the Medical Monitor prior to making decision regarding treatment discontinuation.

ⁱ Every attempt should be taken to assess the blasts count in peripheral blood prior to dosing, however, in circumstances where results are not readily available at the time of planned dosing, the investigator may proceed with dosing provided there are no signs of clinical progression. In this case, results must be evaluated as soon as they become available (but no later than 3 days post dosing). If presence of $\geq 1\%$ blasts in peripheral blood is observed, actions described in table above must be followed immediately.

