9.3. Sample Size and Power Considerations

For the primary efficacy endpoint, HI-E, the sample size is based on one sample binomial exact test. The null hypothesis to be tested is that the proportion of subjects achieving HI-E (defined as ≥ 1.5 g/dL increase in Hgb over any consecutive 56-day period in the absence of RBC transfusions) is $\leq 10\%$; the alternative hypothesis is that the proportion of subjects achieving HI-E is $> 10\%$. With these hypotheses, a sample size of 20 subjects are required with a power of 95% at a one-sided 0.025 alpha level if the expected proportion is 45%. This criterion requires that the lower limit of the 95% confidence intervals for the HI-E rate is greater than 10%.

The selection of a null hypothesis of 10% HI-E rate is based on the results of ARCADE Phase 3 study of darbepoetin, where the proportion of subjects achieving HI-E was reported as 14.7% (95% CI: 8%–25%) (11/75) ([Platzbecker, 2017c](#)). Based on the lower limit of 95% CI, the null hypothesis is assumed as 10%. The expected proportion of 45% HI-E rate is based on the preliminary efficacy observed with luspatercept in the ex-Japan Phase 2 study ([Platzbecker, 2017a](#)). In the study, HI-E rate was 63% (95% CI: 48%–76%) (32/51 evaluable). Based on the lower limit of 95% CI, the expected proportion is assumed as 45%.

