9.6.2. Secondary Efficacy Analyses

The secondary variables will be analyzed descriptively, unless otherwise specified, and will be based on the ITT population and EE population. Kaplan-Meier methods will be used to estimate curves for time to event secondary variables. Counts and percentages will be used to describe categorical variables. Response rate of HI-E per IWG ([Cheson, 2006](#)) within 24 weeks, based on the EE population, will be analyzed as a secondary endpoint.

Modified hematologic improvement - erythroid (mHI-E) per IWG ([Cheson, 2006](#)) is defined as proportion of subjects meeting mHI-E criteria of ≥ 1.5 g/dL mean increase in Hgb compared to baseline that is sustained over any consecutive 56-day period in the absence of RBC

transfusions from W1D1 through Week 24 (and W1D1 through Week 48) of the Treatment Period. Subjects discontinued from the Treatment Period without achieving a mean Hgb increase ≥ 1.5 g/dL will be counted as non-responders.

HI-E per IWG (Cheson, 2006) within 48 weeks is defined as proportion of subjects meeting HI-E criteria of ≥ 1.5 g/dL increase in Hgb sustained over any consecutive 56-day period in the absence of RBC transfusions from W1D1 through Week 48 of the Treatment Period. Subjects discontinued from the Treatment Period without achieving HI-E will be counted as non-responders.

For subjects who have a dose delay meeting the dose modification criterion described in Section 9.6.1, if their Hgb levels temporarily decrease to < 1.5 g/dL but achieve ≥ 1.5 g/dL again after treatment resumption, this period (ie, the time from dose delay to achieving a Hgb increase of ≥ 1.5 g/dL again) will be included as the period of sustained Hgb increase of ≥ 1.5 g/dL.

Time to HI-E will be summarized only for subjects who achieve HI-E. It is defined as time from W1D1 to first onset of achieving ≥ 1.5 g/dL increase in Hgb over any consecutive 56-day period in the absence of RBC transfusions. It will be summarized separately for subjects who achieve HI-E within the first 24 weeks and 48 weeks from W1D1, respectively.

Time to mHI-E will be summarized only for subjects who achieve mHI-E. It is defined as the time from W1D1 to first onset of achieving ≥ 1.5 g/dL mean increase in Hgb over any consecutive 56-day period in the absence of RBC transfusions. It will be summarized separately for subjects who achieve mHI-E within the first 24 weeks and 48 weeks from W1D1, respectively.

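### HI-E and mHI-E bar transfusions only inside the 56-day window, so hemoglobin raised by a transfusion just before it can count toward response

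*Combined protocol and SAP*

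**What the plan says.** **Response.** Protocol 9.6.1 requires for HI-E a "≥ 1.5 g/dL increase in Hgb sustained over any consecutive 56-day period in the absence of RBC transfusions", from W1D1 through Week 24. Section 9.6.2 defines mHI-E by a "mean increase in Hgb compared to baseline that is sustained over any consecutive 56-day period", again without RBC transfusions. The supplied text sets no gap between a transfusion and the start of a window, and excludes no post-baseline hemoglobin value for closeness to a transfusion.

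**Dosing.** Table 5 footnote d (7.2.2) describes a predose value free of transfusion influence as a "Hgb result > 14 days after last RBC transfusion", or one within 3 days from the next transfusion. It is attached to the rows on a hemoglobin rise above 2.0 g/dL and on predose hemoglobin of 12.0 g/dL or more. Section 7.2.2 also judges the hemoglobin target range independently of transfusions.

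**Baseline.** Appendix D asks for pretreatment averages not influenced by transfusion. Its post-treatment criterion has no such wording.

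**Context.** Inclusion criterion 6 requires 16 weeks without RBC transfusion, with a narrow exception for blood loss or infection. Section 8.1.1 allows on-study transfusion at the investigator's discretion, and 6.4.1 records the date of each one. The one sensitivity analysis that 9.6.1 names for HI-E concerns the dose-delay rule. Sections 9.2, 9.6.1 and 9.6.2 leave further detail to the SAP, and the supplied document contains no separate SAP text.

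**The concern.** The protocol protects the baseline and the dosing decisions from transfusion influence but does not say that the response readings are protected. A clean baseline compared with a possibly raised later reading errs in one direction only, toward response. The primary endpoint, mHI-E, and the time to and duration of both are all exposed: onset would be dated too early and duration would be too long. The primary conclusion rests on 20 subjects and a small integer cut-off, so a single borderline subject can matter. mHI-E was added for comparison with the darbepoetin trial (1.3.2.2), so inflation would carry into that comparison.

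**Working it through.** **1. Decision rule and the plan's own power.** Inputs from 9.3 and 9.6.1: n=20, null rate 10%, expected rate 45%, one-sided alpha 0.025, and a test described as "one sample binomial one sided exact test will be performed based on ITT population". For X ~ Bin(20, p):

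| Cut-off r | P(X ≥ r), p=0.10 | P(X ≥ r), p=0.45 |
|---|---|---|
| 5 | 0.0432 | 0.9811 |
| 6 | 0.0113 | 0.9447 |

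The smallest r with a null tail of at most 0.025 is 6. Power is 94.5%, which agrees with the stated 95%. The exact 95% lower limit is 8.7% for 5/20 (below 10%, failure) and 11.9% for 6/20 (success).

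**2. HI-E.** Under footnote d's limit, a window that opens the day after a transfusion can have up to 14 influenced days. The true rise then needs to fill only 56 − 14 = 42 days, so true rises of 42 to 55 days could be read as 56.

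The visit schedule gives the same figure. From Week 4, scheduled readings are 21 days apart. Suppose true rises of at least 1.5 g/dL are read at W16D1, W19D1 and W22D1 (Days 106, 127 and 148), and the rise is lost by Day 169. The true span is 148 − 106 = 42 days, so there is no HI-E. If a transfusion shortly before W13D1 (Day 12 × 7 + 1 = 85) lifts that reading to +1.5 g/dL, the span becomes 148 − 85 = 63 days and HI-E is met. This counts from the first to the last qualifying reading, which is an assumption because the supplied text does not say how days between visits are credited.

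**3. mHI-E.** Since 56/21 = 2.67, a window from Week 4 on holds 2 or 3 scheduled readings. Let the true rise be d at all m readings, and let a transfusion add b to one of them. The mean is d + b/m, so the criterion is met when d ≥ 1.5 − b/m. The documents give no figure for b; 1 to 2 g/dL is assumed.

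| m | b = 1 g/dL | b = 2 g/dL |
|---|---|---|
| 3 | 1.5 − 0.33 = 1.17 | 1.5 − 0.67 = 0.83 |
| 2 | 1.5 − 0.50 = 1.00 | 1.5 − 1.00 = 0.50 |

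**4. Primary test.** One misclassified subject moves the observed rate by 1/20 = 5 percentage points. If a share f of true non-responders is misclassified, the response probability under the null becomes 0.10 + 0.9f. With success at 6 or more:

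| f | Null rate | P(X ≥ 6) |
|---|---|---|
| 0 | 0.100 | 0.0113 |
| 1% | 0.109 | 0.0168 |
| 2% | 0.118 | 0.0241 |
| 3% | 0.127 | 0.0334 |

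The error rate passes 0.025 at f of about 2.1%, an expected 20 × 0.9 × 0.021 = 0.38 subjects. Below that, the conservatism of the exact test absorbs the error. The documents do not allow f to be estimated.

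**The case against.** **The SAP may settle it.** The protocol is silent; it does not state that such values count. That stands, and the point is limited to the supplied text. The protocol did, however, spell out the dose-delay rule and a sensitivity analysis for it, and did neither here.

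**The endpoint follows its sources.** Appendix D limits the no-influence wording to pretreatment values. The darbepoetin definition, as described in 1.1.1.1 and 1.3.2.2, requires 8 weeks without transfusions and mentions no washout. A washout here would make this trial stricter than the benchmark behind its 10% null. This stands as a reason to report both results, but it does not remove the bias.

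**The circumstances are narrow.** For HI-E, a transfusion must fall within 14 days before a reading, and a true rise must follow by the next visit and then end short of 56 days. A transfusion given at a three-weekly visit, after the blood draw, precedes the next scheduled reading by about 21 days and does no harm. Unscheduled samples and weekly rechecks during dose delays would dilute one raised reading. The primary result would also have to sit at the boundary: the probability of exactly 5 responders is 0.9811 − 0.9447 = 3.6% at a 45% rate and 0.0432 − 0.0113 = 3.2% at 10%. All of this stands.

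**Frequency.** A reader might infer from the cited darbepoetin trial, where 36.1% (drug) and 59.2% (placebo) were transfused in weeks 5 to 24, that the problem would be common here. The documents do not support that: that trial admitted subjects receiving fewer than 4 units per 8 weeks, while this one requires transfusion independence.

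**Footnote d is not absolute.** It also accepts values within 3 days from the next transfusion. That limb cannot rescue a reading here: one within 14 days after a transfusion and 3 days before another leaves at most 14 + 3 = 17 transfusion-free days, not 56.

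**Conclusion.** The gap is real and worth closing, as a cheap improvement. As written, the response rule can count a hemoglobin value that the protocol's own 14-day limit treats as transfusion-influenced, and the error always favors response. A reader might infer that a transfusion by itself can create an HI-E responder. It cannot, because about 42 days of true rise are still needed; the effect is confined to borderline cases. mHI-E is more exposed, because a single raised reading shifts the mean.

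The effect on the trial is probably small, since subjects enter transfusion independent, but its frequency is unknown. It could change the primary conclusion only if the true count were at the boundary. The conclusion assumes that the SAP adds no exclusion, that the 14-day limit is a fair measure of influence, and, for the mHI-E figures, a boost of 1 to 2 g/dL on one reading.

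**What to change.** In 9.6.1 and 9.6.2, or in the SAP, state that hemoglobin values taken within 14 days after an RBC transfusion are excluded from HI-E, mHI-E, and the time to and duration of both. No response window may then start before Day 15 after a transfusion. Report the result without this exclusion as a sensitivity analysis, so that the comparison with the darbepoetin benchmark remains available on that trial's definition as described.

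The cost is a few lines of text and one programming filter, since transfusion dates are already collected. A few onsets would move later, and the observed rate may be slightly lower. The sample size, the cut-off of 6 responders and the dosing rules do not change. The rule should be fixed before the primary analysis, so that it is not a post hoc choice in an open single-arm study.

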The primary efficacy endpoint of HI-E per IWG (Cheson, 2006) is defined as proportion of subjects meeting HI-E criteria of ≥ 1.5 g/dL increase in Hgb sustained over any consecutive 56-day period in the absence of RBC transfusions from W1D1 through Week 24. Subjects discontinued from the treatment period without achieving HI-E will be counted as non-responders. Dose modification guidance for luspatercept in Section 7.2.2 defines that, if predose Hgb is ≥ 12.0 g/dL at the day of dosing, the dose should be delayed until Hgb is < 11.0 g/dL. For subjects who meet this criterion and then have their dose delayed, if their Hgb levels temporarily decrease to < 1.5 g/dL but achieve ≥ 1.5 g/dL again after treatment resumption, this period (ie, the time from dose delay to achieving a Hgb increase of ≥ 1.5 g/dL again) will be included as the period of sustained Hgb increase of ≥ 1.5 g/dL.

As the primary efficacy analysis, one sample binomial one sided exact test will be performed based on intent-to-treat (ITT) population, to provide p-value (significance level: 0.025). The number and percentage of subjects who achieve the response and 95% confidence interval (CI) will be presented based on the ITT population.

There is no planned interim analysis for this study.

The primary analysis will be performed when all enrolled subjects have completed 24 weeks of treatment or discontinued before 24 weeks.

Additional follow-up analysis for efficacy and safety will be performed when all subjects have been followed for 5 years from the date of the first dose of IP, or 3 years from the last dose (whichever occurs later) during the Post-Treatment Follow-Up Period of the study.

For more details on statistical considerations please refer to Section 9 of the protocol.

TABLE OF CONTENTS

TITLE PAGE	1
PROTOCOL SUMMARY	6
TABLE OF CONTENTS	12
LIST OF TABLES	18
LIST OF FIGURES	19
1. INTRODUCTION	20
1.1. Myelodysplastic Syndromes	20
1.1.1. Current Treatment Options for Lower Risk MDS.....	21
1.1.1.1. Erythropoiesis Stimulating Agents.....	21
1.1.1.2. Red Blood Cell Transfusions	22
1.1.1.3. Lenalidomide.....	23
1.1.1.4. Hypomethylating Agents	23
1.2. Luspatercept Background	23
1.2.1. Mechanism of Action	23
1.2.2. Nonclinical Studies with Luspatercept	25
1.2.3. Summary of Clinical Experience	25
1.2.3.1. Potential Risks of Human Use	26
1.2.3.2. Overall Benefit Risk Assessment	27
1.3. Rationale	27
1.3.1. Study Rationale and Purpose	27
1.3.2. Rationale for the Study Design	28

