3. OVERALL STUDY DESIGN

3.1. Study Design

The study will be conducted in compliance with the International Council for Harmonisation (ICH) of Technical Requirements for Registration of Pharmaceuticals for Human Use/Good Clinical Practice (GCP) and applicable regulatory requirements.

This is a Phase 2, multicenter, single-arm study to evaluate the efficacy, safety and PK of luspatercept (ACE-536) for the treatment of anemia due to IPSS-R very low, low or intermediate risk MDS in Japanese subjects who are not requiring RBC transfusion.

The study is divided into the Screening Period, a Treatment Period and a Post-Treatment Follow-up Period. See [Figure 2](#) for more details and refer to Section [6](#) for a full list of study procedures/assessments.

Screening Period

Upon giving written informed consent, subjects enter the Screening Period to determine eligibility. Subject screening procedures are to take place within 35 days prior to W1D1. During the Screening Period, subjects will undergo safety and other assessments to determine eligibility for the study. Subjects deemed eligible for the study will be enrolled using integrated response technology (IRT).

Central review of bone marrow aspirate smear and peripheral blood smear will be used to confirm MDS diagnosis according to the WHO 2016 classification ([Appendix B](#)) and to determine the baseline IPSS-R risk classification ([Greenberg, 2012](#)). A bone marrow biopsy will be collected only when adequate aspirate is not attainable.

The sponsor may review key eligibility criteria as well as relevant data (eg, central laboratory reports and cytomorphology/cytogenetic reports) and communicate as necessary with the investigator prior to enrolment of a subject.

Treatment Period

The first dose of IP should be administered on the same day after, but at the latest within 3 days of enrollment.

Subjects will receive IP every 3 weeks (21 days) (ie, at the Week 1 Day 1 (W1D1) Visit, W4D1 Visit; W7D1 Visit, etc.).

Details on IP administration and intra-individual dose titration are outlined in Section [7](#).

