6.4.2. MDS Disease Assessment

The MDS Disease Assessment consists of the investigator's assessment of clinical benefit from IP and status of underlying disease.

The 24-Week MDS Disease Assessment Visit should be completed 24 calendar weeks (ie, Day 169) after W1D1, regardless of dose delays.

As central laboratory results from bone marrow and peripheral blood samples (ie, cytomorphology, cytogenetic analysis) are required as part of the MDS Disease Assessment, a 14-day window is allowed for the 24-Week MDS Disease Assessment Visit (ie, Day 169 ± 14 days) in order to account for sample collection and turnaround time of results.

The MDS Disease Assessment by the investigator, associated with this visit to assess clinical benefit, should be completed no sooner than 24 calendar weeks (ie, 169 days) after W1D1 as it requires 24 weeks of transfusion information in addition to central laboratory results from bone marrow and peripheral blood samples (ie, cytromorphology, cytogenetic analysis). Up to date information related to all transfusions received during the Treatment Period (including those received at outside institutions) must be available prior to completion of the clinical benefit component of the MDS Disease Assessment.

For subjects to remain on treatment beyond this timepoint both of the following criteria must be confirmed in each subject:

- Evidence of clinical benefit defined by either one of the following two criteria:
 - HI-E based on IWG ([Cheson, 2006](#)) ([Appendix D](#)) (Hgb increase of ≥ 1.5 g/dL for the 8 weeks within the 12 weeks immediately preceding Day 169 and every 24 weeks thereafter [ie, Day 337, Day 505, etc.])
 - Maintain RBC transfusion independence
- Absence of disease progression per IWG criteria for altering natural history of MDS ([Cheson, 2006](#)) ([Appendix E](#)) based on central morphological assessment of bone marrow, peripheral blood and cytogenetics results.

Based on the outcome of these assessments, subjects will either be discontinued from treatment with IP and enter the Post-Treatment Follow-up Period or continue open-label treatment as long as above criteria continue to be met or until the subject experiences unacceptable toxicities, withdraws consent, or meets any other discontinuation criteria.

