7.2. Treatment Administration and Schedule

7.2.1. Luspatercept Administration and Schedule

Luspatercept will be administered as a subcutaneous injection every 3 week (21 days; Q3W), at an initial dose level of 1.0 mg/kg. Doses may be titrated up starting at dosing visit W7D1 (ie, Dose 3) as described in Section [7.2.2.](#)

Luspatercept will be administered to subjects by the study staff at the clinical site and administration will be documented in the subject's source record. Subjects must have Hgb, blood pressure and weight assessed (changes of body weight of $\leq \pm 5\%$ do not require a dose adjustment) prior to each IP administration.

Subcutaneous injections will be given in the upper arm, thigh, and/or abdomen. Calculated doses requiring reconstituted volume greater than 1.2 mL should be divided into separate similar volume injections across separate sites using the same anatomical location but on opposite sides of the body (example left thigh and right thigh). The maximum volume per subcutaneous injection should not exceed 1.2 mL.

The injection sites can be rotated according to investigator judgment, and the injections can be given in the following order as needed, for example: 1) right upper arm, 2) left upper arm, 3) right upper thigh, 4) left upper thigh.

Clinical site staff must also confirm (and document in the subject's source record) if any transfusions were received by the subject (including any at outside local institutions in between study visits) prior to each IP administration. In addition to local procedures in place at the site to capture this information, a patient transfusion diary will be provided to subjects and will be reviewed by the site when/if returned by the subject.

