7.2.2. Luspatercept Dose Adjustment and Dose Modification

Appropriate dose adjustments should be made to maintain hemoglobin concentrations within the target range of 10 g/dL to 12 g/dL (6.2 mmol/L to 7.5 mmol/L) independent of transfusions. Starting as soon as with dosing visit W7D1 (ie, Dose 3) of luspatercept, and assessed by the investigator prior to every subsequent luspatercept dosing, subjects may have the dose level increased in a stepwise manner beyond the starting dose of 1.0 mg/kg to 1.33 mg/kg, and up to a maximum of 1.75 mg/kg ([Table 4](#)), if all of the following criteria are met:

- Subject Hgb levels are below the target range of 10 g/dL to 12 g/dL (6.2 mmol/L to 7.5 mmol/L).
- Subject Hgb level increase compared to the Hgb sample taken prior to the previous luspatercept dose is ≤ 1 g/dL.
- The two most recent prior luspatercept administrations assessed must be at the same dose level.
- Subject must not have met protocol dose delay and/or reduction criteria in the two most recent luspatercept administrations (exception of dose delay required due to influence of RBC transfusions). Refer to [Table 5](#).

If all criteria above are met, the dose may be increased by 1 dose level. The dose level should be titrated individually for each subject and must not exceed 1.75 mg/kg. Starting dose with dose increases and reductions are presented below for reference ([Table 4](#)).

Dose delay and/or reduction or discontinuation may be required due to increased hemoglobin or adverse events. For details on dose modification guidance for luspatercept please refer to [Table 5](#).

Table 4: Luspatercept Starting Dose Level with Dose Reductions and Dose Titration

3rd Dose Reduction	2nd Dose Reduction	1st Dose Reduction	Starting Dose Level	1st Dose Titration Increase	2nd Dose Titration Increase
0.45 mg/kg	0.6 mg/kg	0.8 mg/kg	1.0 mg/kg	1.33 mg/kg	1.75 mg/kg

Table 5: Luspatercept Dose Modification: Dose Delay, Dose Reduction, and Discontinuation Guidelines

Event at the Day of Dosing (Assessed prior to each IP administration at the respective visit ⁱ)	Action
Any suspected related AE \geq Grade 3 ^{a,b}	Dose delay ^c until resolved to \leq Grade 1 or baseline, and then reduce dose by one dose level according to Table 4
> 3 dose reductions due to suspected related AE ^a	Discontinue treatment

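### Does Section 9.6.1 have to state how days between three-weekly hemoglobin readings count toward the 56-day response?

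*Combined protocol and SAP*

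**What the plan says.** Section 9.6.1 defines response as a rise of at least 1.5 g/dL, an "increase in Hgb sustained over any consecutive 56-day period in the absence of RBC transfusions from W1D1 through Week 24". Appendix D likewise asks that a response last at least 8 weeks. Neither gives a minimum number of readings or a rule for the days between them.

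Section 9.6.1 does deal with interruptions. When a dose is delayed because predose hemoglobin is 12.0 g/dL or more and the rise is temporarily lost, "the time from dose delay to achieving a Hgb increase of ≥ 1.5 g/dL again) will be included as the period of sustained" response. A sensitivity analysis without this credit is planned.

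The reading schedule comes from other sections:

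- Section 3.1 sets dosing every 21 days, and Section 7.2.1 requires a reading before each dose ("Subjects must have Hgb, blood pressure and weight assessed").
- Table 3 also lists hematology at W2D1 and W3D1.
- Table 5, footnote d, covers delays: "Hgb should be rechecked weekly during dose delay".
- Section 6.4.2 says the 24-week disease assessment "should be completed 24 calendar weeks (ie, Day 169) after W1D1, regardless of dose delays", with a window of 14 days either side.

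Section 9.2 leaves time windows and endpoint-analysis rules to the SAP, and Section 9.6.1 leaves its additional details there too.

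**The concern.** Fifty-six is not a multiple of 21, so a run of three-weekly readings never matches the required period exactly, and someone must decide what an unobserved day is worth. Two programmers could take the same readings and disagree on whether a subject responded. With 20 subjects and a cut-off of six, one such disagreement can change the result of the primary test.

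The study is single-arm, so nothing masks the accumulating readings. A rule chosen after seeing them would not be protected by the nominal level. The planned sensitivity analysis removes only the dose-delay credit, and the modified endpoint based on the mean rise is a different quantity, so neither settles the point.

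The edges of the 24 weeks and of the credit raise the same question. The last titration step takes effect late, so its response depends on which reading is the last to count. The credit has no stated limit and no stated date by which the rise must be regained.

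**Working it through.** **The plan's own figure.** Section 9.3 gives n = 20, null rate 10%, expected rate 45%, one-sided level 0.025 and power 95%. With X ~ Binomial(20, p):

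- P(X ≥ 5 | 0.10) = 0.0432, above 0.025. The exact lower 95% limit for 5/20 is 8.7%.
- P(X ≥ 6 | 0.10) = 0.0113, below 0.025. The exact lower 95% limit for 6/20 is 11.9%.
- The cut-off is therefore six responders, and power is P(X ≥ 6 | 0.45) = 0.945. The stated 95% reproduces after rounding.

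**Readings needed.** Without delays the dosing-visit readings after baseline fall on Day 1 + 21j: Days 22, 43, 64, 85, 106, 127, 148 and 169. Take k consecutive qualifying readings, with visits allowed to move by 2 days.

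| Counting rule | Days credited | Fewest readings | Check |
|---|---|---|---|
| First to last reading must span the period | 21(k − 1) | 4 | k = 3 gives 42, at most 46; k = 4 gives 63, at least 59 |
| Each reading stands until the next | 21k | 3 | k = 2 gives 42, at most 46; k = 3 gives 63, at least 59 |
| Any 56-day window free of a failing reading | 21(k + 1) − 1 | 2 | k = 1 gives 41, at most 45; k = 2 gives 62, at least 58 |

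The third rule would accept two readings 21 days apart with failures on both sides. That is a strained reading of a sustained rise, so the practical choice is between four readings and three.

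**The last eligible reading.** Twenty-four weeks are 24 × 7 = 168 days. If Day 168 were the limit, a run starting on Day 106 would end at Day 148, a span of 148 − 106 = 42 days, and would fail the span rule. Section 6.4.2, however, equates 24 calendar weeks with Day 169. A run to that visit spans 169 − 106 = 63 days and passes.

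This covers the titration worry on the scheduled days. Section 7.2.2 states: "The two most recent prior luspatercept administrations assessed must be at the same dose level". With 1.0 mg/kg on Days 1 and 22 and 1.33 mg/kg on Days 43 and 64, the top level starts on Day 85 at the earliest. The next dosing-visit reading is Day 106.

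**The credited gap.** Suppose a dose is delayed on Day 148 and resumed at the first weekly recheck, Day 155. The next dosing visit is 155 + 21 = Day 176, a gap of 176 − 148 = 28 days. Day 176 is after Day 169 but inside the assessment window, which closes on Day 169 + 14 = 183. Whether a reading that late counts is not stated.

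**What the choice might do.** If a stricter rule lowered the true rate, P(X ≥ 6) would be 0.874 at 40%, 0.755 at 35% and 0.584 at 30%. How far the rate would fall cannot be derived from the documents. A simulation with assumed half-life, lag, slope variation and reading error, scaled so that the three-reading rule gives about 45%, produced:

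| Rule | Response rate | P(X ≥ 6) |
|---|---|---|
| Span rule, readings to Day 171 | 34–44% | 71–94% |
| Three-reading rule | 44–48% | 93–97% |

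The two rules gave different trial verdicts in 1.2–23.5% of simulated trials. A separate simple model, with reading SD 0.4–0.7 g/dL, gave about 27% against 38% when the mean rise levels off at 1.5 g/dL. At a plateau of 2.5 g/dL it gave 82–97% against 89–99%.

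**The case for a change.** The best argument for amending the plan is that it would be cheap and the verdict is sensitive. One paragraph would fix the rule, and one misclassified subject can move 6/20 to 5/20. The protocol itself shows that response definitions matter. Section 1.1.1.1 reports that responders in the epoetin alfa trial rose from 27/85 (31.8%) to 39/85 (45.9%) when modified criteria were applied post hoc. Section 1.3.2.2 gives difficulty in interpreting the criteria as the reason for the dose-delay credit. On this view the sponsor settled the ambiguity affecting delayed subjects and left the one affecting stretches of ordinary three-weekly readings.

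Much of this stands. No rule for days between readings appears in Sections 1.3.2.2, 6.4.2 or 9.6.1, Table 2 or Appendix D. The counts of four and three are correct. The start, limit and closing date of the credited gap are open.

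Other parts do not stand. The protocol does say how a credited gap counts: the whole period is treated as sustained response. Section 6.4.2 already ties Week 24 to Day 169. The simulated losses depend on scaling the three-reading rule to 45%, and nothing in Section 9.3 says that 45% was derived under that rule. Section 9.3 sets 45% below an observed 63% (32/51). If the largest simulated shortfall, 45 − 29 = 16 points (span rule, readings to Day 168 only), were taken from 63%, the rate would be 47% and P(X ≥ 6) would be 0.96.

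**Conclusion.** No change to the plan is needed. This is derivation detail that the protocol expressly leaves to the SAP, and analysts settle it routinely when they program the endpoint. Because the SAP text is not in the document reviewed, the most that can be said is that the protocol is silent; it cannot be said that the plan lacks a rule. No rule the plan does state has been shown to give a wrong answer.

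The exact test holds its level under either counting rule, provided one is fixed before the readings are examined. The Protocol Summary sets the timing: "The primary analysis will be performed when all enrolled subjects have completed 24 weeks of treatment or discontinued before 24 weeks". The derivation has to be settled before then under the existing deferral.

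Putting a particular rule into Section 9.6.1 would be a trade-off and not a clear gain. Requiring four readings observes both ends of the 8 weeks but may reduce power, to 71–94% in a simulation on outside assumptions. Requiring three avoids that but observes only 42 of the 56 days. A hard cut-off such as Day 171 (Day 169 plus the 2-day visit window) would drop readings from assessments validly held on Days 172 to 183. It would also add a limit on the credit that Section 9.6.1 does not contain.

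The possible effect is not trivial, since one subject separates p = 0.043 from p = 0.011. The four-or-three count applies only to stretches without a delay, because readings are weekly during one. The sample size of 20, the cut-off of six and the test all stand.
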